#### 3a. Selection criteria:

Male and female patients who have been diagnosed as having Type 2 diabetes mellitus for a minimum period of 6 months, who are interested in seeking Ayurvedic treatment as sole treatment or as complimentary treatment to western medical treatment and meet the following criteria will be selected to participate in this study.

1. Onset of diabetes mellitus for six months.
2. Aged between 30 and 65 years
3. Stable glycaemic control over the preceding 2-3 months. They will be initially selected from a range of HbA1c varying from 7 – 14 and the individual subject should not have a variation of >20% between the previous HbA1c and the HbA1c done at the commencement of the study

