#### 4a Primary outcome variable

- I. Glycaemic control evaluated with HBA1C carried out centrally with ion exchange HPLC and the units will be NGSP standard.
- II. Serious liver and kidney adverse events when taking the biscuits containing the extract of *Salacia reticulata*.

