## 6. SAMPLE SIZE & RANDOMIZATION

1. Consecutive patients who seek treatment for diabetes mellitus will be screened for eligibility.
2. Those who are eligible will be invited for the study.
3. Sample size calculation:

Sample size was initially calculated by using a formula specific for crossover studies (9). The standard deviation (0.9) to calculate the standard error was taken from the baseline data (7). Clinically significant improvement of HbA1c in the intervention group over the placebo group was estimated as 0.5 units of HbA1c (difference in means). As this gave very low sample size (13 in each arm) we calculated the sample size for parallel studies according to Pocock (10). Significance level (alpha) 0.05 and power (1-beta) = 0.8 giving rise total of 51 patients were in each arm. With anticipated dropout rate of 10%, 112 patients were estimated sample size for a single center study

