## 7. STATISTICAL ANALYSIS (10)

1. Being a cross over trial, the analysis will be done as a paired analysis.
2. Intention to treat analysis.

3. Formal tests for period effect, treatment effect, carryover effect and interaction between treatment and period will be carried out.

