#### 8. PROCESS OF THE TRIAL

After running period where stability of HBA1C is assured patients will be randomized to receive either a standard preparation of Kothala himbutu biscuits or a placebo, a similar biscuit without the extract of *Salacia reticulata*. The study product and the placebo will be given to the participants and the investigators and the participants will be blinded to the treatment.

Four biscuits will be taken as a mid morning and afternoon snack, at 10am and 4 pm respectively. Oral hypoglycemic treatment for diabetes taken at the time of recruitment will be continued but subject to change if the condition of the patient changes, as determined by treating clinician.

Patients will continue treatment for a period of seven months separated by a washout period of one month at cross over. On completion of the first three months on either treatment or placebo patients will not receive either placebo or biscuit with the active ingredient during a wash out period of one month. The wash out period is determined as one month to minimize the carry over bias. In the event that significant difference exists between the two groups at the end of three months, the study will be terminated at that point.

During this time the subjects will have a minimum of eight to ten visits inclusive of the booking visit and will meet with a medical officer at each visit for review of glycaemic control and other possible complications. A six-point blood glucose profile (pre and post breakfast, pre and post lunch, pre and post dinner samples) will be performed on one day during the week prior to each visit.

HBA1C will be performed at recruitment, at three months and on completion of the study at seven months. Existing oral medication and doses for diabetes mellitus will be adjusted as requested during the study.

In the event that the clinical investigators feel that significant deterioration of glycaemic control has occurred or that the patient would require a step up to insulin, patients will be withdrawn from the study.

Specific written instructions will be provided for the timing of snacks in the standard dosage. Counting the unused biscuits will assess compliance. All adverse events will be recorded. Patient preference for the biscuits will also be assessed.

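### No HbA1c is scheduled when a patient is withdrawn for worsening glycaemia, so the paired analysis in effect uses completers and would modestly understate a real difference between the biscuits

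*Combined protocol and SAP*

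**What the plan says.** - **Withdrawal.** Section 8 (Process of the trial) provides that, if the investigators feel significant "deterioration of glycaemic control has occurred or that the patient would require a step up to insulin, patients will be withdrawn from the study". The trigger is a judgement with no numeric threshold, and withdrawal is from the study, not only from the biscuit.
- **HbA1c timing.** The same section says that HbA1c "will be performed at recruitment, at three months and on completion of the study at seven months". The visit schedule (8 a) lists it at V1, V2, V8, V12 and V13. There is no early-withdrawal visit, and nothing says that withdrawn patients attend V13.
- **Outcome.** HbA1c is the first of two primary outcome variables (4a), "carried out centrally with ion exchange HPLC and the units will be NGSP standard".
- **Analysis.** Section 7 states "Being a cross over trial, the analysis will be done as a paired analysis" and, as a separate item, "Intention to treat analysis". It defines no analysis set and gives no rule for a missing period.
- **Allowance for loss.** Section 6: "With anticipated dropout rate of 10%, 112 patients were estimated sample size for a single center study".
- **Stop rule.** Section 8 ends the study if the two groups differ significantly at three months.
- **Limits on such withdrawals.** Section 3a requires that "the individual subject should not have a variation of >20% between the previous" HbA1c and the one at study start. Section 3b excludes insulin users. Section 8 adds: "Existing oral medication and doses for diabetes mellitus will be adjusted as requested during the study".

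The text between 8a and 8c of the monitoring section was not available and could not be checked.

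**The concern.** The rule removes patients because the quantity behind a primary outcome has worsened. Glycaemia is reviewed at every visit, so removal can come before the end-of-period HbA1c. A paired difference needs both end-of-period values, and the plan offers no other route for a patient who lacks one. Labelling the analysis intention to treat does not supply values that were never measured.

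If one biscuit is better, more patients cross the withdrawal threshold on the other. The patients who show the difference most clearly then leave the comparison, and the estimate moves toward zero, whether the extract helps or harms. The 10% added to the sample size replaces numbers but does not correct selective loss. The first-period comparison that can stop the study is affected too, because withdrawals at V6 and V7 have no V8 value.

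**Working it through.** **The plan's own figures (section 6: difference 0.5, SD 0.9, alpha 0.05, power 0.8; two-sided assumed)**
- Parallel: n per arm = 2 × (0.9 × 2.80 / 0.5)² = 50.9, so 51. Total 102; 102 × 1.10 = 112.2, so 112. Reproduced.
- Crossover: (0.9 × 2.80 / 0.5)² = 25.4 in total, about 13 per sequence. Reproduced, with 0.9 used as the SD of the paired difference.

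**Who is lost**

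| Withdrawn at | End of period 1 (V8) | End of period 2 (V12) | Usable pair |
|---|---|---|---|
| V6, V7 | missing | missing | no |
| V9, V10, V11 | present | missing | no |

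**Size of the shrinkage (simulation)**

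From the documents: true difference 0.50, SD 0.9 for a single HbA1c. Assumed, because the documents are silent: correlation ρ of 0.6–0.8 between a patient's HbA1c values; withdrawal signal = r × standardized change from baseline + √(1 − r²) × noise, with r of 0.5–1.0; cut-off set to give the stated total loss; no second period after a first-period withdrawal. The estimate is half the difference between sequences in the mean of (period 1 − period 2) among complete pairs.

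| Total loss under this rule | Complete-pair estimate of 0.50 |
|---|---|
| 10% (about 11 of 112) | 0.449–0.490 |
| 5% | 0.469–0.494 |
| 2.5% | 0.481–0.497 |

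- With no true difference, the estimate stays within 0.001 of zero.
- At 10% loss, 6.6–9.0% of patients are withdrawn on the worse biscuit (about 7–10 of 112) and 1.0–3.4% on the better one (about 1–4).
- Wider assumptions (SD of the paired difference 0.7–1.27, r 0.7 or 0.99) give about 0.43–0.47 at 10% loss, 0.40–0.45 at 20% and 0.37–0.44 at 30%. None of these figures is a bound.

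**Final paired test, 101 pairs**
- SD of the difference = 0.9 × √(2(1 − ρ)): 0.569 at ρ = 0.8 and 0.805 at ρ = 0.6. Standard error = SD/√101 = 0.057–0.080, so the largest shift in the table (0.051) is below one standard error.
- Power at 0.45 is at least 0.9998 for these SDs and 0.9987 if the SD is 0.9. With an SD of 1.27 and 10% withdrawn, simulated power is 95–96%.

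**Three-month between-group comparison** (two-sided 0.05 t-test assumed, since the plan names no test or level; SD 0.9)
- With 10% total loss, about 5% falls in period 1, and the first-period difference becomes 0.454–0.489.

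| Per arm | Power at 0.50 | Power at 0.455 |
|---|---|---|
| 51 | 0.793 | 0.715 |
| 56 | 0.830 | 0.755 |

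**What a remedy recovers (10% loss)**
- Mixed model, no added HbA1c: 0.450–0.488; with V2 included, 0.442–0.487. No gain.
- Period-end HbA1c added, new therapy without effect: 0.483–0.496 without V2 and 0.500–0.502 with V2.
- Period-end HbA1c added, new therapy lowering it by an assumed 0.5 or 1.0 (with V2): 0.470–0.487 or 0.439–0.474. The effect of biscuit plus therapy is then itself 0.461–0.484 or 0.421–0.468.
- Withdrawal value only, carrying one third to two thirds of the effect (with V2): 0.490–0.500 for benefit and 0.477–0.491 for harm. There is no gain for harm at r = 0.5 with one third carried (about 0.482 against 0.488 for complete pairs).

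**The case against.** The strongest reply is that this matters little. The shifts are below one standard error, the lower end at 10% needs the whole all-cause dropout to come from one rule and a withdrawal signal that tracks HbA1c perfectly, and stability screening, exclusion of insulin users and oral-drug adjustment should keep such withdrawals few. That stands as to size. It does not remove the point: the bias has a direction, follows from a written rule, touches a primary outcome, and an HbA1c that was not drawn cannot be recovered later.

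Second, using the period-end value whatever the therapy can land further from 0.50 than complete pairs do (0.439–0.474 against 0.449–0.490 when therapy lowers HbA1c by 1.0). This stands, and it is why the target has to be stated first.

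Third, reliance on completers is an inference, since section 7 lists intention to treat beside the paired analysis and defines neither. That is so, but the plan describes no way for an unpaired patient to contribute.

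Fourth, the six-point glucose profiles before each visit could inform missing HbA1c values. They could be used as auxiliary data; this was not tested, the plan does not provide for it, and they are not the primary outcome.

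A reader might infer more: that the trial is biased toward a false positive, that its final test lacks power, or that the withdrawal rule is itself wrong. The documents support none of these. There is no bias without a difference, the paired test has ample power, and the clinical rule is not in question here.

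**Conclusion.** The concern holds in a limited form. Following the plan as written loses patients selectively on a primary outcome and leaves an analysis that is in effect of completers. If the biscuits differ, the estimated biscuit effect shrinks modestly: 0.50 to about 0.45–0.49 if all of the planned 10% loss came from this rule, and to 0.47–0.50 at 2.5–5%. The size is conditional on the assumed correlations and withdrawal signal, and loss above 10% would give more.

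It would be too strong to say that power is safe throughout. That is true of the final paired test. The three-month comparison that can stop the study has about 79–83% power at 0.50 and 72–76% at 0.455, with 51–56 per arm. It would also be too strong to say that an added HbA1c restores 0.50 in general: how much is recovered depends on the target and on the effect of any new therapy. The change should be made, because it is cheap and cannot be made afterwards.

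**What to change.** Leave the decision to withdraw or to change therapy with the investigators as written, and change only measurement and analysis.

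1. Draw HbA1c at the visit where withdrawal is decided, without delaying treatment, and with consent again at the scheduled end of the current period.
2. State the target before unblinding: the effect of the biscuit alone, or of the biscuit together with any changed therapy.
3. Analyse all randomized patients with any post-randomization HbA1c in a linear mixed model with period and biscuit effects and a random patient effect, with the V2 HbA1c as a pre-treatment response. Where therapy changed, use the withdrawal value if the target is the biscuit alone, or the period-end value if it is biscuit plus therapy. Report the other choice, and complete pairs, as sensitivity analyses.
4. Include withdrawn patients' HbA1c in the three-month comparison.
5. Report withdrawals and oral-drug changes by biscuit.

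Cost: at 10% loss, about 11 assays at withdrawal and up to 11 more at period end (11 to 22 in all), a short consent and protocol change, and analysis-plan wording. Limits: recovery is partial where only an early withdrawal value exists, because HbA1c lags, and the mixed model without the added HbA1c does not remove the bias.

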##### 8 a. Visit Schedule

##### V1 - Selecting patients and Recruitment

- Check for inclusion and exclusion criteria
- Informed written consent form signed
- Obtain demographic data
- History and examination
- Dietary advice
- Screening investigations
  - FBC, liver profile, renal profile, FBS, HbA1c, ECG, Urine for microalbumin
- V2 - 8 weeks after V1
  - Review investigation reports of V1 in relevance with exclusion criteria
  - 2nd HbA1c, Lipid profile, UFR
- V3 Trace laboratory reports
  - Provision of a glucometer
  - Glucometer Training and self-monitoring of blood glucose
- V4 Randomization
  - Checking for glucometer capability
  - Review the blood sugar series
  - History and examination
  - Providing biscuit
- V5 - May be over the phone (1 week after providing biscuit)
  - Evaluate the compliance for the biscuit
- V6 - 1month after providing biscuit
  - Evaluate the blood sugar series
  - History and examination
  - Review dosage of other drugs
  - Provide stock of biscuit for 1 month
  - SGPT, SGOT, Serum creatinine
- V7 - 2months after providing biscuit
  - Evaluate the blood sugar series
  - Trace laboratory reports
  - History and examination
  - Review dosage of other drugs
  - Provide stock of biscuit for 1 month
  - SGPT, SGOT, Serum creatinine
- V8 - 3 months after providing biscuit
  - Stop biscuits

History and examination  
Trace the laboratory reports  
Review dosage of other drugs  
SGPT, SGOT, Serum creatinine, HbA1c, FBS, Urine for microalbumin  
1 month washout period

V9 - 1 month after stopping biscuits  
Evaluate the blood sugar series  
History and examination  
Trace the laboratory reports  
Review dosage of other drugs  
Change to other group of biscuit (provide biscuit for 1 month)  
SGPT, SGOT, Serum creatinine

V10 1 month after changing biscuits  
Evaluate the blood sugar series  
History and examination  
Trace laboratory reports  
Review the dosage of other drugs  
SGPT, SGOT, Serum creatinine  
Provide stock of biscuit for 1 month

V11 2 month after changing biscuits  
Evaluate the blood sugar series  
History and examination  
Trace laboratory reports  
Review dosage of other drugs  
SGPT, SGOT, Serum creatinine  
Provide stock of biscuit for 1 month

V12 3 month after changing biscuits  
History and examination  
Trace laboratory reports  
Review dosage of other drugs  
SGPT, SGOT, Serum creatinine, HbA1c, FBS, Urine for microalbumin

V13 9 months after changing biscuits  
HbA1c

8a. Ethics and informed consent

Written informed consent will be obtained from the patients and ethical clearance obtained from the Ethics Review Committees of Peradeniya Medical Faculty and Rajarata Medical Faculty.

The trial will be registered with the International Standard Randomized Controlled Trial Number Register.

#### 8. TRIAL MONITORING

##### 8a. Data monitoring & Safety Board

Independent data and safety monitoring board will regularly review interim data from the trial. The composition of this body is as follows.

1. [name] MBBS MD, Senior Lecturer & head Department of Medicine FMAS, RUSL.
2. [name] MBBS MD MSc Associate Professor in Community Medicine Peradeniya Medical Faculty.

##### 8c Conduct of trials:

The trial will be conducted at the medical clinic of the Department of Medicine, Faculty of Medicine & Allied Sciences, and Rajarata University of Sri Lanka at Teaching Hospital Anuradhapura under the direct supervision of [name].

#### 9. DATA AND SAMPLE COLLECTION

The data will be entered into a structured questionnaire and will contain demographic data as well as a detailed history regarding the course, treatment and control of diabetes mellitus in individual patients. All blood samples will be immediately transported to a pre-planned, selected laboratory for analysis. Each sequential data item will be added to the patient records maintained in written (structured questionnaire) and computer data base forms (Microsoft Access) either on line or uploaded to the central database within 5 working days of receipt.

#### 10. DATA ANALYSIS AND PRESENTATION:

There will be interim analysis of data after the end of first treatment period. to observe the progress of each patient to ensure good glycaemic control. Standard statistical packages will be used in data analysis. Patient flow will be presented in a CONSORT diagram.

